#### **8.1.1 Adverse Drug Reaction**

All noxious and unintended responses to a medicinal product related to any dose should be considered an adverse drug reaction. “Response” to a medicinal product means that a causal

relationship between a medicinal product and an adverse event is at least a reasonable possibility, ie, the relationship cannot be ruled out.

### 8.1.2 Unexpected Adverse Drug Reaction

An unexpected adverse drug reaction is defined as an adverse reaction, the nature or severity of which is not consistent with the applicable product information. For ETX2514SUL, the reference safety information is included in the Investigator's Brochure currently in force.

### 8.1.3 Assessment of Adverse Events by the Investigator

The unblinded Investigator will assess the severity (intensity) of each adverse event as mild, moderate, or severe. In Part A, in addition to the unblinded Investigator, a blinded assessor will also be responsible for the causality assessment, and as detailed below.

#### Assessment of severity:

Mild – An event that is easily tolerated and generally not interfering with normal daily activities.

Moderate – An event that is sufficiently discomforting to interfere with normal daily activities.

Severe – An event that is incapacitating with inability to work or perform normal daily activities.

#### Causality assessment:

The relationship of an adverse event to the administration of the study drug is to be assessed by the blinded assessor and the unblinded Investigator for Part A and by the unblinded Investigator for Part B, according to the following definitions:

No (unrelated, not related, no relation) – The time course between the administration of study drug and the occurrence or worsening of the adverse event rules out a causal relationship and another cause (concomitant drugs, therapies, complications, etc) is suspected.

Yes (related) – The time course between the administration of study drug and the occurrence or worsening of the adverse event is consistent with a causal relationship and no other cause (concomitant drugs, therapies, complications, etc) can be identified.

The definition implies a reasonable possibility of a causal relationship between the event and the study drug. This means that there are facts (evidence) or arguments to suggest a causal relationship.

The following factors should also be considered:

- The temporal sequence from study drug administration-
  - The event should occur after the study drug is given. The length of time from study drug exposure to event should be evaluated in the clinical context of the event.
- Underlying, concomitant, intercurrent diseases-
  - Each report should be evaluated in the context of the natural history and course of the disease being treated and any other disease the patient may have.
- Concomitant drug-
  - The other drugs the patient is taking or the treatment the patient receives should be examined to determine whether any of them might be recognized to cause the event in question.

- Known response pattern for this class of study drug-
  - Clinical and/or preclinical data may indicate whether a particular response is likely to be a class effect.
- Exposure to physical and/or mental stresses-
  - The exposure to stress might induce adverse changes in the recipient and provide a logical and better explanation for the event.
- The pharmacology and PK of the study drug-
  - The known PK properties (absorption, distribution, metabolism, and excretion) of the study drug should be considered.

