#### 5.4.1 Unblinded Investigator

An unblinded Investigator at each site will evaluate criteria for clinical outcomes, conduct causality assessment for adverse events, and assess clinical signs and symptoms at study visits for patients in both Part A and Part B. For patients in Part A, a blinded assessor will also evaluate criteria for clinical outcomes, conduct causality assessment for adverse events, and assess clinical signs and symptoms at study visits. The unblinded Investigator must be a qualified physician, able to perform medical evaluations, and determine medical diagnoses (eg, Principal Investigator, sub-Investigator). For consistency, whenever possible, the same unblinded Investigator should complete all unblinded assessments for a study patient. If there is a discrepancy between the assessment of the blinded assessor and unblinded Investigator, the assessment from the blinded assessor will be used. If there is a missing assessment from either the blinded assessor or unblinded Investigator, the other available assessment will be used. An adjudication committee may be organized for endpoint adjudication should it be deemed necessary by the DSMB. In such a case, a charter will be developed that describes their activities.

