#### 8.1.4 Adverse Events of Special Interest

Adverse events of special interest will be analyzed, summarized, and reported in the clinical study report. Statistical comparisons will be made between the investigational and control groups in Part A.

Adverse events of special interest and their definitions include the following:

- Allergic and hypersensitivity reactions: Severe and serious adverse drug reactions from the Medical Dictionary for Regulatory Activities (MedDRA) Standardized MedDRA Queries of allergy and hypersensitivity;
- Nephrotoxicity: Using the RIFLE criteria for the duration of the study (see Table 6), and
- Emergent infections and superinfections: All serious and severe events in the MedDRA system organ class of infections and infestations other than the indication infection (ie, ABC).

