#### 9.2.4 Analysis of Safety

All patients who receive any amount of study drug (MITT Population) will be included in the safety analyses. Patients who received the wrong study drug for their entire course of treatment will be analyzed in the group based on the drug received.

A primary analysis of safety will be performed for Part A to assess the proportion of patients with nephrotoxicity, as measured by the RIFLE criteria based on the Safety and CE Populations.

Overall safety will be assessed for Part A and Part B in the Safety Population. The number and percentage of patients in each treatment group reporting at least 1 occurrence of a TEAE for each unique system organ class and preferred term will be tabulated. A TEAE is defined as an adverse event occurring on or after the administration of the first dose of study drug. Treatment-emergent adverse events will also be tabulated by treatment group, severity, and the relationship to study drug as assessed by the Investigator. The number and percentage of patients in each treatment group reporting at least 1 occurrence of a treatment-emergent SAE will be tabulated. The number and percentage of patients (in each treatment group) prematurely discontinuing study drug treatment due to a TEAE will be tabulated by system organ class and preferred term. Adverse events of special interest in Part A will be summarized for all patients by treatment.

Safety laboratory data will be presented by descriptive statistics of the post-baseline value and the change from baseline, as well as the number and percentage of patients with potentially clinically significant laboratory values. Descriptive statistics of vital signs and ECG parameters and the change from baseline will also be presented. An outlier analysis of the ECG parameters will be conducted.

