#### 9.4.1. Adverse Events

A treatment-emergent adverse event (TEAE) is defined as an adverse event occurring on or after the administration of the first dose of study drug. An overview of adverse events will be provided which summarizes the incidence of the following categories:

- All AEs,
- All TEAEs,
- Drug-related TEAEs,
- TEAEs by severity,
- SAEs,
- Drug-related SAEs,
- SAE leading to death,
- TEAE leading to discontinuation of study drug, and
- SAE leading to discontinuation of study drug.

Patients with multiple events will be counted only once within each category. Severity grade and relationship will be counted using the maximum severity and the strongest relationship respectively for a patient with multiple TEAEs.

The number and percentage of patients reporting a TEAE in each treatment group will be tabulated by SOC and PT; by SOC, PT, and severity; and by SOC, PT, and relationship (related or unrelated to study drug and imipenem/cilastatin). Summary tables will be presented alphabetically by SOC and decreasing frequency of PT in the EXT2514SUL group within SOC. For all analyses of TEAEs, if the same AE (based on PT) is reported for the same patient more than once, the AE is counted only once for that PT and at the highest severity and strongest relationship to study drug.

The number and percentage of patients reporting a drug-related TEAE, a SAE, a treatment emergent SAE, a drug-related treatment-emergent serious adverse event (TESAE), and a TEAE leading to discontinuation of study drug in each treatment group will be summarized by SOC and PT.

A list of patients who have SAEs, a list of patients who discontinue from study drug, and a list of death will be provided. All adverse events will be listed.

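### The two causality levels in Protocol 8.1.3 leave out an event with consistent timing and a possible other cause, and the literal *Yes* conflicts with the standard in 8.1.1

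*Protocol*

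**What the plan says.** The causality part of Protocol 8.1.3 offers two levels, each made of two conditions joined by *and*.

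- *No*: the time course "rules out a causal relationship and another cause (concomitant drugs, therapies, complications, etc) is suspected".
- *Yes*: the time course "is consistent with a causal relationship and no other cause (concomitant drugs, therapies, complications, etc) can be identified".

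The text then adds: "The definition implies a reasonable possibility of a causal relationship between the event and the study drug". A list of factors follows, including underlying disease and other drugs. It tells the rater to look for competing causes but not which level applies when one is found.

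Protocol 8.1.1 sets the standard for an adverse drug reaction: a causal "relationship between a medicinal product and an adverse event is at least a reasonable possibility, ie, the relationship cannot be ruled out".

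On who rates, Protocol 5.4.1 and SAP 3.3.1 list causality among the blinded assessor's duties in Part A. The same paragraph says: "If there is a discrepancy between the assessment of the blinded assessor and unblinded Investigator, the assessment from the blinded assessor will be used". Protocol 9.2.4 and the Synopsis safety paragraph instead tabulate "the relationship to study drug as assessed by the Investigator", and under Protocol 5.4 the Principal Investigator is unblinded. SAP 9.4.1 tabulates relationship without naming a rater. SAP 9.3.2 repeats the precedence rule only for clinical outcome.

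**The concern.** A rater who follows 8.1.3 exactly has no level for an event that fits the drug in time but could also have another cause. In severely ill patients with permitted concomitant drugs, that situation should be familiar. Two careful raters can both follow the protocol and disagree: one calls the event related under 8.1.1, the other declines because another cause can be named.

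The rating feeds several outputs:

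- the drug-related TEAE, SAE and treatment-emergent SAE tables in SAP 9.4.1;
- potentially the hypersensitivity events of special interest, which Protocol 8.1.4 limits to "Severe and serious adverse drug reactions" and for which it promises a Part A comparison;
- the reporting of related serious events more than 30 days after the last dose (Protocol 8.3);
- the classification of suspected unexpected reactions (Protocol 8.5).

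A smaller, linked issue is the rater. If the unblinded rating is tabulated in Part A, the comparison of related events is made with knowledge of treatment, and Protocol 1.4 calls colistin's nephrotoxicity and neurotoxicity well described.

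**Working it through.** The plan gives no figure to reproduce. The check is one of logical coverage, followed by a comparison of the standards.

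**Coverage.** Cross timing with other cause and compare each cell with the literal definitions in Protocol 8.1.3.

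| Timing | Other cause | Level under 8.1.3 |
|---|---|---|
| Causality excluded | Suspected | *No* |
| Consistent | None identified | *Yes* |
| Consistent | Possible | Neither |
| Causality excluded | None | Neither |

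Two of the four cells have no level. Only the third matters in practice, since nobody would call an event related when its timing excludes a link.

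**Standards side by side, for the third cell.**

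- Literal *Yes* in 8.1.3: not met, because another cause can be identified.
- Literal *No* in 8.1.3: not met, because timing does not exclude a link.
- Reasonable-possibility sentence in 8.1.3: where the possibility is reasonable, points to related.
- Definition in 8.1.1: related whenever the link cannot be excluded.

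The literal *Yes* therefore conflicts with 8.1.1 and with the sentence that follows it.

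**What happens downstream.** SAP 9.4.1 reports only related or unrelated and has no rule for an event that fits neither. SAP 9.1.2 leaves missing values of other variables unimputed, so a relationship left blank is not counted as related.

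**Size.** Let *a* be the share of events in the second cell and *p* the share in the third. If raters follow 8.1.1, the related share is *a* + *p*. If they treat any nameable cause as excluding *Yes* and default to *No*, it is *a*. The difference is *p*. The documents give neither *p* nor the proportion of third-cell events that would be rated *No*; that proportion could be anything from 0% to 100%. Assuming a value for *p*, say 50% to 90%, only returns that value as the maximum shift.

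**The case against.** A reader might infer that related events will be under-called. The documents do not establish that direction. For an event in the gap, *No* is barred as firmly as *Yes*, and the remaining text (8.1.1 and the reasonable-possibility sentence) points towards related. What is established is room for inconsistency, with under-calling as the result of one particular reading.

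A reader might also infer that the imipenem/cilastatin given to every patient makes *Yes* nearly unattainable. That is not supported. Protocol 5.1 lists imipenem/cilastatin among the study drugs, and SAP 9.4.1 tabulates relationship to it as well as to study drug, so it is not clearly a concomitant drug that blocks *Yes*. Nor are all patients in intensive care: Protocol 4.1.1 provides for enrolment outside it.

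Nor does it follow that serious reactions go unrecorded. Protocol 8.3 requires every serious event up to 30 days after the last dose to be reported within 24 hours of the site learning of it, whatever its cause. The DSMB reviews serious events and deaths on an ongoing basis (Protocol 9.3), and Protocol 8.5 gives deaths their own plausibility test. Within that window the label is at risk, not the event. The hypersensitivity category uses the term that 8.1.1 defines broadly, so its exposure is only potential.

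On the rater, the word Investigator in 9.2.4 may be loose usage, since the heading of 8.1.3 uses the same word for a section covering both raters. That softens the conflict but does not settle it: no analysis text says which rating is tabulated.

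**Conclusion.** The point holds as a defect of definition. The two levels are not exhaustive, and the literal *Yes* contradicts the protocol's own standard in 8.1.1 and in 8.1.3. Events with consistent timing and a possible other cause may be classified inconsistently between raters, and under-called if the no-other-cause condition is taken at its word. This conclusion needs no numerical assumption, only the plain reading of *and* in the two definitions. The size of any effect cannot be computed from the documents.

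The exposed outputs are those listed above. Twenty-eight-day mortality, the RIFLE nephrotoxicity comparison, the tables of all treatment-emergent events and the capture of serious events within 30 days do not depend on the rating. The unclear rater for Part A is a real but lesser issue. Both should be corrected; neither threatens the primary efficacy or primary safety analysis.

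**What to change.** 1. In Protocol 8.1.3, redefine the levels to be exhaustive and to match 8.1.1. *Yes*: there is a reasonable possibility that the drug caused the event, so a link is not excluded, even if another cause is possible. *No*: there is no reasonable possibility.
2. In Protocol 9.2.4 (with the Synopsis) and SAP 9.4.1, state that Part A relatedness is tabulated on the blinded assessor's rating, with the Investigator's used where that is missing, as Protocol 5.4.1 and SAP 3.3.1 already provide. Show the Investigator's rating in a supplementary table, and say how an event with neither rating is counted.

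Both ratings are already required in Part A, so no new type of data is needed, but the cost is more than wording and a site memo:

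- More events may be rated related, and more expedited reports may follow.
- SAP 7.1 describes the first intense PK sampling in the past tense, so patients have been treated. Events rated under the present wording need re-rating, or flagging by definition version.
- Protocol 5.4.2 limits the blinded assessor's chart access and withholds treatment group and dosing frequency, while 8.1.3 asks raters to weigh class effects and pharmacology. The supplementary Investigator table is there for that reason.

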#### 8.1.4 Adverse Events of Special Interest

Adverse events of special interest will be analyzed, summarized, and reported in the clinical study report. Statistical comparisons will be made between the investigational and control groups in Part A.

Adverse events of special interest and their definitions include the following:

- Allergic and hypersensitivity reactions: Severe and serious adverse drug reactions from the Medical Dictionary for Regulatory Activities (MedDRA) Standardized MedDRA Queries of allergy and hypersensitivity;
- Nephrotoxicity: Using the RIFLE criteria for the duration of the study (see Table 6), and
- Emergent infections and superinfections: All serious and severe events in the MedDRA system organ class of infections and infestations other than the indication infection (ie, ABC).

**Table 6. Definition of RIFLE Criteria**

Term	Definition
Risk (R)	Increased creatinine level 1.5× or GFR decrease >25%
Injury (I)	Increased creatinine level 2× or GFR decrease >50%
Failure (F)	Increased creatinine level 3×, GFR decrease >75%, or creatinine level ≥4 mg/dL
Loss (L)	Persistent acute renal failure or complete loss of function for >4 weeks
ESKD (E)	ESKD for >3 months
ESKD = end-stage kidney disease; GFR = glomerular filtration rate; RIFLE = Risk–Injury–Failure–Loss–End-stage renal disease.	

## 8.2 Serious Adverse Events

An adverse event or adverse reaction is considered serious if, in the view of either the Investigator or Sponsor, it results in any of the following outcomes:

- Death;
- A life-threatening adverse event;

Note: An adverse event or adverse reaction is considered “life-threatening” if, in view of either the Investigator or Sponsor, its occurrence places the patient at immediate risk of death. It does not include an event that, had it occurred in a more severe form, might have caused death.

- Requires hospitalization or prolongation of existing hospitalizations;

Note: Any hospital admission with at least 1 overnight stay will be considered an inpatient hospitalization. An emergency room visit without hospital admission will not be recorded as an SAE under this criterion, nor will hospitalization for a procedure scheduled or planned before signing of informed consent. However, unexpected complications and/or prolongation of hospitalization that occur during elective surgery should be recorded as adverse events and assessed for seriousness. Admission to the hospital for social or situational reasons (ie, no place to stay, live too far away to come for hospital visits) will not be considered inpatient hospitalizations. Adverse events recorded for a patient who is hospitalized for treatment of the underlying illness, do not necessarily meet serious criterion of hospitalization.

- A persistent or significant disability/incapacity or substantial disruption of the ability to conduct normal life functions;
- A congenital anomaly/birth defect; or
- An important medical event.

Note: Important medical events that may not result in death, be life-threatening, or require hospitalization may be considered an SAE when, based upon appropriate medical judgment, they may jeopardize the patient and may require medical or surgical intervention to prevent 1 of the outcomes listed above. Examples of such medical events include allergic bronchospasm requiring intensive treatment in an emergency room or at home, blood dyscrasias or convulsions that do not result in inpatient hospitalizations, or the development of drug dependency.

### **8.3 Serious Adverse Event Reporting – Procedures for Investigators**

#### Initial reports

All SAEs occurring from the time of the main informed consent (not the limited scope ICF) or randomization until 30 days following the last administration of study drug must be reported to Medpace Clinical Safety within 24 hours of the knowledge of the occurrence (this refers to any adverse event that meets any of the aforementioned serious criteria). This is to be understood that Investigators should report any SAE occurring from the time the main ICF (including all study procedures) was signed. Investigators are not required to report SAEs occurring for patients who only signed the limited scope ICF (which only allows rapid testing on a respiratory sample). All SAEs that the Investigator considers related to study drug occurring after the 30-day follow-up period must be reported to the Sponsor. All SAEs should be reported as if it were a blinded study and without evidence of treatment assignment on the report.

To report the SAE, complete the SAE form electronically in the electronic data capture (EDC) system for the study. When the form is completed, Medpace Safety personnel will be notified electronically and will retrieve the form. If the event meets serious criteria and it is not possible to access the EDC system, send an email to Medpace Safety at [[contact]](mailto:[contact]) or call the Medpace SAE reporting line (telephone number listed below), and fax the completed paper SAE form to Medpace (fax number listed below) within 24 hours of awareness. When the EDC system becomes available, the SAE information must be entered within 24 hours of the system becoming available.

**Follow-up reports**

The Investigator must continue to follow the patient until the SAE has subsided or until the condition becomes chronic in nature, stabilizes (in the case of persistent impairment), or the patient dies.

Within 24 hours of receipt of follow-up information, the Investigator must update the SAE form electronically in the EDC system for the study and submit any supporting documentation (eg, patient discharge summary or autopsy reports) to Medpace Clinical Safety via fax or e-mail. If it is not possible to access the EDC system, refer to the procedures outlined above for initial reporting of SAEs.

**8.4 Pregnancy Reporting**

If the patient or partner of a patient participating in the study becomes pregnant during the study or within 120 days of discontinuing study drug, the Investigator should report the pregnancy to Medpace Clinical Safety within 24 hours of being notified. Medpace Clinical Safety will then forward the Exposure In Utero form to the Investigator for completion.

A patient becoming pregnant while on study drug will immediately be withdrawn from the study and early study termination procedures will be performed.

The patient or partner should be followed by the Investigator until completion of the pregnancy. If the pregnancy ends for any reason before the anticipated date, the Investigator should notify Medpace Clinical Safety. At the completion of the pregnancy, the Investigator will document the outcome of the pregnancy. If the outcome of the pregnancy meets the criteria for immediate classification as an SAE (ie, postpartum complication, spontaneous abortion, stillbirth, neonatal death, or congenital anomaly), the Investigator should follow the procedures for reporting an SAE.

